This will be a randomized control trial to study the efficacy of a combined lidocaine and corticosteroid injection on pain, range of motion, and patient reported outcomes versus a corticosteroid injection alone for the treatment of common upper extremity tendinopathies and nerve entrapments that are often treated with a combination of these injectates. Patients will be assigned randomly to a control group (corticosteroid injection alone) or the treatment group (lidocaine plus corticosteroid injection). At the initial injection a 10-point likert scale prior to and after the injection will be administered. The patients will be followed up at 6 weeks after the injection, at which time the Visual Analog Scale for pain (VAS-pain), range of motion (ROM), and patient reported outcome data will be collected and any complications will be noted. Patients will also utilize a pain journal to track VAS-pain over the first 7 post-injection days. We hypothesize that those who receive lidocaine plus corticosteroid injection will be non-inferior in regards to pain, range of motion (ROM), failure of injection requiring surgery, and patient reported outcome scores compared with patients who received corticosteroid injection alone.

Background and Significance:

Tenosynovitis is a common ailment of the upper extremity resulting in pain around the affected joint due to injury to the tendon sheath. One of the most common manifestations of tenosynovitis is trigger finger. Trigger finger is an extremely common pathology encountered by primary care providers and hand surgeons. Reported incidence of 28 cases per 100,000 has been documented [1]. This entity occurs when the contents of the flexor tendon sheath do not fit cleanly

within the sheath, causing friction on movement of the fingers. Progression from a clicking or locking sensation to complete inability to flex or extend the finger (hence the designation “trigger finger”) occurs over the course of the disease. Therefore, triggering may not be initially noted on exam. Pain from this pathology can be experienced at the proximal interphalangeal joint, the metacarpophalangeal joint, or even the palm [2]. Reported increases in rates have been documented in diabetics, cases of repetitive trauma, those with renal and thyroid disease, and individuals with inflammatory conditions [3].

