The cause of trigger finger is poorly understood, with early studies identifying the condition as a form of tenosynovitis on histologic analysis. More recent studies have identified a lack of inflammatory cells, suggesting an abnormality in proliferation of fibrocartilage rather than a primary inflammatory condition [4]. Treatment of trigger finger has been studied extensively, but few evidence based guidelines exist for the treatment of this disease process [1]. Current treatment modalities are diverse and numerous, including non-operative management (splinting, stretching techniques, heat therapy, electric stimulation therapy, acupuncture, corticosteroid injection, and high-intensity focused ultrasound aimed at degrading the fibrosis surrounding the tendon sheath) and operative management (with open, percutaneous, and endoscopic methodology all having been described) [1, 5]. In 2017, Amirfeyz *et al.* proposed an evidenced based treatment guideline for trigger finger, with the first line treatment listed as “steroid and local anesthetic injection” followed by open operative management upon either failure of corticosteroid injection or patient refusal of corticosteroid injection [1].

This treatment algorithm reflects existing research regarding treatment of trigger finger: corticosteroid injection for trigger finger has been studied extensively [6-25]. However, few well, randomized control trials have been undertaken comparing corticosteroid injection to placebo. Of the trials that have been done, both studies indicated improved outcomes with a combined injectate of corticosteroid with lidocaine versus just lidocaine alone [26, 27]. The long term efficacy of steroid injection is reasonable, with success rates as high as 69% [8]. That said, many patients will experience return of their symptoms and will go on to need open surgical treatment for recurrent trigger finger [3].

While several studies have compared corticosteroid injection with lidocaine to lidocaine injection alone, to date, no study has evaluated the effectiveness of a corticosteroid injection either with or without lidocaine. Our study aims to evaluate whether or not lidocaine in the injectate combined with corticosteroid improves patient reported outcomes and recurrence of pain and morbidity from trigger finger as compared with corticosteroid injection alone.

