2. Determine differences in range of motion of the affected joint in the corticosteroid plus lidocaine group as compared to the corticosteroid alone group.
3. Determine differences in patient-reported outcome scores (VAS-pain, qDASH, PRWE, ASES, SF12, EQOL) in the corticosteroid plus lidocaine group as compared to the corticosteroid alone group.
4. Report patient characteristics associated with efficacy of addition of lidocaine to corticosteroid injectate for pain and ROM resolution (type of injury, affected joint, age, BMI, comorbidities, etc.).

Hypotheses:

Hypothesis⁰: Corticosteroid injectate alone will result in statistically significant reduced pain scores as compared to corticosteroid with lidocaine for the treatment of tenosynovitis.

Hypothesis¹: Lidocaine plus corticosteroid injectate will result in equivalent requirements for repeat injection or conversion to surgery as compared with corticosteroid injectate alone for the treatment of tenosynovitis.

Hypothesis²: Lidocaine plus corticosteroid injectate will result in equivalent patient reported outcomes scores as compared to corticosteroid alone for the treatment of tenosynovitis.

Hypothesis³: Lidocaine plus corticosteroid injectate will result in equivocal patient-reported outcome scores, ROM, and pain reduction as compared to corticosteroid alone for the treatment of tenosynovitis.

Study Design

This will be a randomized control trial of a group of patients with upper extremity tenosynovitides treated with either lidocaine plus corticosteroid or corticosteroid injection alone by upper extremity fellowship trained surgeons at Emory University. Patients will be randomly assigned to one of two groups at the time of treatment: 1. Lidocaine Plus Corticosteroid and 2. Corticosteroid Alone. A random allocation sequence, concealed in consecutively numbered, opaque, sealed envelopes, determining active treatment or placebo, will be computer generated. Written-informed consent will be obtained from patients prior to injection.

Patients in the Corticosteroid group will be treated with a 40 mg/mL injection of corticosteroid following sterile preparation. The volume of injectate differs for each tenosynovitis being treated. For example, trigger finger patients in the corticosteroid alone group will receive a 1mL of injectate total (consisting of 1 mL of 40mg/mL triamcinolone).

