Patients in the Corticosteroid and Lidocaine group will be treated with a 40 mg/mL injection of corticosteroid combined with 1% lidocaine. The volume of injectate differs for each tenosynovitis being treated. For example, patients being treated for trigger finger will receive 0.5 mL of 1% lidocaine and 1 mL of 40mg/mL triamcinolone.

Needle size and insertion site of needle differs for each tenosynovitis being treated. For trigger finger specifically, needle injections will be performed with an appropriately sized needle inserted over the A1 pulley at a 45-degree angle. The injection will be done with the same technique for both groups by the attending physician. The medication will be injected extra-synovially in order to make the treatment more reproducible. This method of injection has been supported in previous studies.

Outcome Measures:

- Likert Scale: A 10-point likert scale will be asked before and after injection which has been previously validated in other studies looking at efficacy and pain surrounding injections of the upper extremity.
- Pain Assessment: A pain assessment will be assessed before performing the injection, at the time of injection, and at each subsequent follow up visit. Pain scores will be obtained via the Visual Analog Pain Scale (VAS-pain), which is ranked from 0 (no pain) to 10 (highest amount of pain). Pain will be assessed at rest and active movement of the affected joint. Patient will also be asked to fill out the VAS-pain score twice daily in a pain journal (once in the morning and once at night) each day until post-injection day 7.
- qDASH/PRWE/ASES/SF12/EQOL score: These scores will be administered at each clinic follow up. They will also be administered 6 week after the injectate has been performed.
- Need for subsequent reinjection and surgical operation will be recorded.

These scores, specifically the 10-point likert, will also be assessed before performing the injection, immediately after the injection, and again at the various follow up appointments. During clinic follow up we will monitor for complications.

Inclusion Criteria:

- All adult clinical patients of Emory upper extremity surgeons undergoing injection for treatment of the following who are willing to participate in the study will be included in the study: Tenosynovitis of the upper extremity, including but not limited to, the shoulder, biceps, elbow, wrist, thumb, carpometacarpal, midcarpal, elbow, and small joints of the hand (PIP, DIP, MP).

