As stated above, the first line treatment for trigger finger is corticosteroid injection with lidocaine, although there are a significant proportion of hand surgeons who inject corticosteroid alone. As no study has evaluated the efficacy of lidocaine mixed with the injectate versus corticosteroid alone, our study does not constitute deviation from current status quo of best medical practice for the treatment of trigger finger. **Both treatment options are considered standard of care and it is solely based on physician preference for which regimen is chosen as an injectate.** Patients will be notified of any potential risks with signed written consent as they would before any standard corticosteroid injection for the treatment of trigger finger. They will also be asked to sign an additional consent form agreeing to participate in our study outlining the nature of the study and the fact that no deviation from current best medical practice will occur throughout the course of the study.

Benefits to future subjects or science

By identifying whether or not lidocaine combined with corticosteroid injectate leads to improved patient outcomes as compared with corticosteroid injection alone, we will be able to educate physicians and patients on best medical practice for treatment of trigger finger. Additionally, as lidocaine has been reported to cause significant burning during injection, if there is no additional benefit to addition of lidocaine to corticosteroid injection, we will be able to spare future patients the discomfort of combining the injectate with lidocaine.

Data safety and monitoring plan:

Patients will be followed up closely in clinic at 2 weeks and 6 weeks post-injection to ensure patients did not experience side effects from the injection and to assess for efficacy of the injection. A low dose of corticosteroid and lidocaine is being utilized and we do not anticipate adverse effects.

Patients will have the ability to remove themselves from this study either completely or partially, and these options will be elucidated on the written consent form.

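### Hypothesis 1 claims equivalent need for reinjection or surgery, but the outcome has no observation window, scheduled follow-up ends at 6 weeks, and no margin is set

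*Combined protocol and SAP*

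**What the plan says.** Under Hypotheses, the protocol states: "Lidocaine plus corticosteroid injectate will result in equivalent requirements for repeat injection or conversion to surgery as compared with corticosteroid injectate alone". The Precis/Abstract frames a related claim as non-inferiority: the combined injection "will be non-inferior in regards to pain, range of motion (ROM), failure of injection requiring surgery, and patient reported outcome scores".

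Under Outcome Measures, the outcome receives one undated line: "Need for subsequent reinjection and surgical operation will be recorded". Statistical Analysis adds only that repeat injection and surgical release are among the variables collected.

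On timing, the Precis/Abstract says "The patients will be followed up at 6 weeks after the injection", and the data safety and monitoring plan says "Patients will be followed up closely in clinic at 2 weeks and 6 weeks post-injection". Outcome Measures mentions further follow-up appointments but dates none of them later than 6 weeks.

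Statistical Analysis specifies a chi-square test for proportions, significance at P < .05 and 95% confidence intervals. It gives no equivalence or non-inferiority margin for any outcome.

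On the course of the disease, Background and Significance says of trigger finger: "The long term efficacy of steroid injection is reasonable, with success rates as high as 69" per cent, and that "many patients will experience return of their symptoms and will go on to need open surgical treatment for recurrent trigger finger".

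**The concern.** The sequence that the background describes is relief, then relapse, then another injection or an operation. A plan whose last dated contact is at 6 weeks may miss much of it. The text can be read in two ways, and each leaves a gap:

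- **Recording stops at 6 weeks.** The hypothesis then concerns only early failures, although it is worded without a time limit.
- **Recording is open-ended.** Patients enrolled early are then observed longer than those enrolled late, and the resulting proportion describes no stated period.

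Under either reading there is no margin, so the plan does not define what result would count as *equivalent*. What is at stake is an unqualified statement that lidocaine does not change the need for further treatment, resting on data that may cover only part of the relevant period.

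**Working it through.** **The plan's own figure.** The only sample size calculation is for VAS-pain at injection (difference 1, SD 2). With two-sided alpha 0.05 and 80% power (the power is not stated; 80% is inferred because it reproduces the figure):

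n = 2 × [2 × (1.960 + 0.842) / 1]² = 62.8, so 63 per arm.

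The figure of 63 reproduces as a per-arm number. It says nothing about reinjection or surgery, for which no calculation is given.

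**Inputs for Hypothesis 1**

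- Total enrolment is 1000 (Statistical Analysis). Allocation of 1:1 is assumed, giving 500 per arm.
- Long-term failure is at least 1 − 0.69 = 31%. This comes from Background and Significance, applies to trigger finger only, and has no horizon beyond long term.
- The comparison rate of 41%, a 10-point gap, is assumed for illustration.
- The fraction f of failures that have occurred by 6 weeks is not in the documents. It is assumed equal in both arms and varied from 10% to 50%.
- The chi-square test is taken as two-sided at 0.05.

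**Formula**

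Power = Φ[(|p1 − p2| − 1.96 × SE0) / SE1], with SE0 = √[2 p̄(1 − p̄)/n] and SE1 = √{[p1(1 − p1) + p2(1 − p2)]/n}.

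For f = 1 and n = 500: SE0 = 0.03036, SE1 = 0.03019, and (0.10 − 0.0595)/0.03019 = 1.34, so power is 91%.

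For f = 0.10: the rates are 3.1% and 4.1%, SE0 and SE1 are both 0.01178, and (0.010 − 0.0231)/0.01178 = −1.11, so power is 13%.

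| Share of failures by 6 weeks | Rates compared | Gap (points) | Power, 500 per arm | Power, 63 per arm |
|---|---|---|---|---|
| 10% | 3.1% v 4.1% | 1.0 | 13% | 5% |
| 25% | 7.75% v 10.25% | 2.5 | 28% | 7% |
| 50% | 15.5% v 20.5% | 5.0 | 54% | 11% |
| 100% | 31% v 41% | 10.0 | 91% | 21% |

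Exact enumeration of the chi-square test at 500 per arm agrees with the normal approximation to the nearest percentage point. An arcsine approximation gives 14% rather than 13% in the first row. The last column matters because the plan also analyses each diagnosis separately, with a target of 63; it reads 63 as per arm, which the plan does not say.

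**What a margin would require.** For two one-sided tests judged by a 95% confidence interval, with 80% power and no true difference:

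n per arm = 2p(1 − p)(1.960 + 1.282)² / margin².

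| Failure rate | 5-point margin | 10-point margin |
|---|---|---|
| 2% | 165 | 42 |
| 5% | 400 | 100 |
| 10% | 757 | 190 |
| 31% | 1799 | 450 |

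These margins are assumptions. A short window with few events makes an absolute margin easy to meet while saying little about later failure. At 31% failure, 500 per arm would suffice for a 10-point margin but not for a 5-point one. A longer window therefore does not by itself support the word *equivalent*.

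**The case against.** Several stronger readings are tempting, and the documents do not support them.

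- **Equivalence would be declared by default.** A reader might infer this from the chi-square test and the missing margin. The plan nowhere says that a non-significant result will be read as equivalence, and it provides for 95% confidence intervals.
- **Hypothesis 1 could not be shown wrong.** This is too strong. With 500 per arm, a doubling from 5% to 10% is detected with about 86% power. For a 1.5-fold difference, at assumed reference rates of 2 to 5%, the chance of a non-significant result is about 62 to 83%: likely, not certain.
- **Few events always mean low power.** This depends on holding the ratio fixed. For a fixed 5-point gap at 500 per arm the order reverses: about 98% power at a 2% reference rate, 86% at 5% and 39% at 31%. The better-founded concern is that later failures go uncounted.
- **Six weeks is too early, as a fact.** The documents give no time course of failure. That many failures come later is an inference from the background's wording. The 69% figure is for trigger finger, while the trial pools many diagnoses.
- **Recording stops at 6 weeks.** The line under Outcome Measures is undated, so this is not stated.
- **Open-ended recording invalidates the comparison.** With concurrent randomisation, differences in follow-up should balance between arms. What is lost is the meaning of the rate, not the validity of the test.

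It is also fair to say that the powered outcome is VAS-pain at injection, and that choosing any particular longer window is partly a matter of judgement. What stands after all this is the missing window and the undefined claim of equivalence.

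**Conclusion.** The point holds in a limited form. Hypothesis 1 makes an unqualified equivalence claim about an outcome with no observation window, in a plan whose last scheduled visit is at 6 weeks and which sets no margin. Failures after 6 weeks may go uncounted, or the reported rate will have no defined horizon.

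The 13 to 54% range for pooled power, against 91% with full ascertainment, rests on the assumed 31% v 41% contrast, an assumed 10 to 50% of failures by 6 weeks in both arms, and 1:1 allocation. It illustrates the possible loss and is not an estimate of it.

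This should be changed because it concerns a named hypothesis. It does not touch the primary outcome.

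**What to change.** 1. Set one observation window, counted from injection, for all patients. Twelve months is only an example: the background cites it for de Quervain tendinopathy, where benefit lasted among responders, and that does not establish it as the right horizon here.
2. Define the event (reinjection, surgery or either) and say how patients lost before the window ends are handled.
3. Take the events from the medical record, using the record number already collected. The plan removes identifiers once data collection is complete, so this must be arranged before then.
4. Report the risk difference with its 95% confidence interval. Do not conclude equivalence from a non-significant chi-square. Use *equivalent* or *non-inferior* only against a justified margin fixed in advance.
5. If the longer window is declined, restrict Hypothesis 1 to the first 6 weeks and drop *equivalent*.

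The cost is one chart review per patient (1000 in all), changes to IRB and consent wording, and a later analysis of this outcome. No extra visits are needed. Care received elsewhere would be missed in both arms. The fallback in item 5 costs only wording.

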- Between the ages of 18 years and 95 years.

- For trigger finger: patients with a diagnosis of stenosing tenosynovitis based on a history of triggering and the presence of tenderness over the A1 pulley upon clinical examination. All patients, based on the Quinnell grading of trigger finger see in the figure below, will be included.

Grade	Clinical findings (during flexion and extension)
0	Normal movement
I	Uneven movement
II	Actively correctable
III	Passively correctable
IV	Fixed deformity

Exclusion Criteria:

- Patients who are minors, vulnerable subjects, or who are not willing to consent to participate in the study.
- Allergies to glucocorticoids, current daily use of glucocorticoids or strong opioids (morphine, fentanyl, hydromorphone, ketobemidone, methadone, nicomorphine, oxycodone, and meperidine), severe diabetic neuropathy of the hand influencing pain perception, rheumatoid arthritis, and neurological or psychiatric diseases, potentially influencing pain perception.
- Subjects who, in the opinion of the investigator, may be non-compliant with study schedules or procedures.

Statistical Analysis:

Data will be stored on an excel spreadsheet. We will collect the name, medical record number, age at time of surgery, ethnicity, gender, BMI, presence of diabetes, Quinnell grading of trigger finger, smoking status, pre-injection VAS-pain, post-injection VAS-pain, 10 point likert scale, complications, and need for repeat injection or surgical release. It is possible that other variables may be added depending on analysis. Each variable will be used as a nominal variable when possible (e.g. smoking status) or a continuous variable if needed (e.g. VAS-pain, patient related outcome scores). For some statistical calculations we may break up the continuous variables in to ranges (e.g. Ages 15-20, 25-30). We will perform statistical analysis using unpaired, 2-tailed Student t test to compare means for normally distributed data, Kruskal-Wallis test to compare medians of non-normally distributed data, and chi-square test to compare proportions. Statistical significance will be interpreted as $P < .05$. Confidence intervals will be calculated with a confidence level of 95%.

Specifically, the 2 groups will be compared using the Mann-Whitney U test to analyze the difference between the post-injection VAS scores. The Wilcoxon sign-rank test will be used to test the difference between the treatment and control group for pain and patient related outcomes.

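### Coding preference and unfixed cut points leave age and BMI open to post hoc banding in Objective 4

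*Combined protocol and SAP*

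**What the plan says.** In the combined protocol and SAP, the Statistical Analysis section gives a coding rule: "Each variable will be used as a nominal variable when possible", with smoking status as the example. The examples it attaches to continuous use are pain and patient-reported scores: "a continuous variable if needed (e.g. VAS-pain, patient related outcome scores". Age and BMI appear in the list of data to be collected but are not named as continuous.

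The next sentence allows banding: "For some statistical calculations we may break up the continuous variables in to ranges (e.g. Ages 15-20, 25-30". It gives no other cut points, for age or for anything else.

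Under Inclusion Criteria the eligible range is "Between the ages of 18 years and 95 years".

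Objective 4 is to "Report patient characteristics associated with efficacy of addition of lidocaine to corticosteroid injectate", with the candidates listed as "type of injury, affected joint, age, BMI, comorbidities, etc".

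The tests listed are the t test, Kruskal-Wallis, chi-square, Mann-Whitney U and Wilcoxon signed-rank tests. The section states no regression or interaction model.

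**The concern.** Objective 4 asks whether the effect of adding lidocaine varies with patient characteristics. Two of those it names, age and BMI, are measured on a continuous scale. Three features of the plan together steer them into categories: the stated preference for nominal coding, the permission to cut continuous variables into ranges, and a list of tests with no model in which a continuous covariate could enter.

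Two things are at stake. The first is power: coarse bands discard information, and many bands treated as unordered spend degrees of freedom. The second is error control: with no cut points fixed in advance, they can be chosen after seeing which ones give P < .05. The one example offered does not help, because its bands do not match the eligible age range and are not contiguous.

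**Working it through.** **The plan's own figure.** The only design figure is 63, for a 1-point VAS difference with SD 2. With two-sided alpha 0.05 and 80% power (the power is assumed; the plan does not state it), n per arm = 2 × SD² × (1.960 + 0.842)² / difference² = 2 × 4 × 7.849 / 1 = 62.8, so 63. It reproduces as a per-arm number. Nothing below depends on it or changes it.

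**Example bands against eligibility.** The eligible integer ages 18 to 95 number 78. The band 15-20 begins three years below the minimum. Between 15-20 and 25-30, ages 21, 22, 23 and 24 fall in no band; 20 and 25 are end points and are covered.

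**Information kept.** The documents give no age distribution and no effect size for Objective 4, so this step and the next are illustrative. Assume a normally distributed covariate with a linear effect. The share of information kept is the squared correlation between the covariate and its band mean.
- Median split: 2/π = 0.637, about 64%. With 1000 patients, that is equivalent to about 640. If the covariate were uniform instead, the share would be about 75%.
- Four equal groups: about 86%.
- Contiguous 10-year bands, age about N(58, 13) assumed: about 95%.
- Contiguous 5-year bands, same assumption: about 99%.

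**Power of the interaction test.** Scale the true interaction so that continuous age (1 df) has 80% power, which makes the noncentrality (1.960 + 0.842)² = 7.849. For a banded analysis, multiply by the share kept and use a noncentral chi-square with (bands − 1) df at alpha 0.05. Eight 10-year bands or sixteen 5-year bands, starting at 18, cover the eligible range.

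| Coding of age | Share kept | df | Noncentrality | Power |
|---|---|---|---|---|
| Continuous | 1.00 | 1 | 7.85 | 80% |
| Median split | 0.637 | 1 | 5.00 | 61% |
| Quartiles, unordered | 0.86 | 3 | 6.75 | 57% |
| 10-year bands, unordered | 0.95 | 7 | 7.46 | 47% |
| 5-year bands, unordered | 0.99 | 15 | 7.77 | 35% |

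Coarse bands lose power through lost information. Fine bands lose it because unordered coding ignores the ordering of age and spends degrees of freedom.

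**Free cut points.** In a simulation of 1000 patients with no true interaction and age about N(58, 13) (both assumed), an age interaction was declared if any one of four cuts (40, 50, 60 or 70) gave P < .05. The false-positive rate was about 16%, against 5% for one cut fixed in advance. The four cuts are an assumption too; the plan names none.

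**The case against.** The strongest reply is that the coding sentence, read with its examples, only follows natural type: smoking status is nominal, and pain and scores are continuous. The following sentence treats some variables as continuous and offers banding as an occasional option. If conversion to categories were the default, that sentence would hardly be needed. The bands are only an example of format. Age and BMI are to be collected, and nothing says that only bands will be recorded, so any loss can be avoided at analysis.

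Most of this stands, and it rules out several stronger readings.
- A reader might infer that the plan will categorise its continuous variables and so will lose information. The wording permits this but does not commit to it.
- A reader might infer that baseline pain is at risk in the same way. VAS-pain and the patient-reported scores are already named as continuous, although the optional banding sentence could in principle reach them.
- A reader might extend the two bands into a repeating pattern and conclude that about half of the ages would be unclassified. The documents give no such pattern. Even if it were repeated, eight gaps of four years would leave 32 of 78 integer ages (41%) uncovered.
- A reader might take 64% as the loss-adjusted information under this plan. The plan mentions no median split, and the one band width it illustrates would keep about 99% if the bands were contiguous.

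The reply does not answer three things: the unfixed cut points, the omission of age and BMI from the variables named as continuous, and the lack of any listed analysis that could use them as continuous.

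**Conclusion.** The point holds as a permitted weakness in the analysis of Objective 4. The coding preference, the open-ended banding and the group-comparison tests together make post hoc categories the natural route for age and BMI, and the example bands conflict with the plan's own age range. The primary VAS comparison and the sample size of 63 are untouched.

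The size depends on what the analysts do. On the stated assumptions, an interaction detectable with 80% power on continuous age would have about 61% power after a median split and about 35% with sixteen unordered 5-year bands. Choosing among four cuts after the fact would roughly triple the false-positive rate. These figures rest on a linear interaction, an assumed age distribution and assumed banding schemes, none of which the documents give. They illustrate what the wording allows; they do not predict what the trial will lose.

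**What to change.** In the Statistical Analysis section:

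1. For Objective 4, regress the outcome on treatment, the characteristic and their interaction, with age and BMI entered as continuous variables. The model has to be stated, because rewording the coding rule alone would leave no listed analysis that could take a continuous covariate.
2. Keep VAS-pain and the patient-reported scores continuous, as already named.
3. Use bands only in descriptive tables, contiguous over 18-95 and fixed before the data are examined.
4. Delete the example bands.

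This is a free improvement. Age and BMI are already to be collected, so no extra patients, visits or data are needed; the only cost is a few sentences and a little more analysis work.

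### Pre-injection VAS is collected but not used in any named comparison of the arms, and the pooled analysis has no diagnosis term: a cheap, optional gain in precision, not an error

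*Combined protocol and SAP*

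**What the plan says.** Under Outcome Measures, "A pain assessment will be assessed before performing the injection, at the time of injection, and at each subsequent follow up visit". The same item adds: "Pain will be assessed at rest and active movement of the affected joint". The variable list in Statistical Analysis includes "pre-injection VAS-pain, post-injection VAS-pain, 10 point likert scale".

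That section names four tests that could compare VAS between the arms:

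- an unpaired two-tailed t test for normally distributed data;
- a "Kruskal-Wallis test to compare medians of non-normally distributed data";
- a "Mann-Whitney U test to analyze the difference between the post-injection VAS scores";
- a signed-rank test: "Wilcoxon sign-rank test will be used to test the difference between the treatment and control group".

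None is given a covariate, and no regression or ANCOVA is named. The section also says "Confidence intervals will be calculated with a confidence level of 95" per cent. The last hypothesis speaks of "ROM, and pain reduction as compared to corticosteroid alone", but the plan does not say whether any test is on raw scores or on change from baseline.

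The sample size paragraph makes VAS pain at the moment of injection the primary outcome, for a 1-point difference with SD 2. It aims for 63 patients per diagnosis and 1000 in all. Patients are to be analysed together and also in subgroups by primary diagnosis. No diagnosis term or stratified test is named for the analysis of all patients together.

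**The concern.** Part of the spread in pain scores after an injection may simply reflect how much pain patients had before it. Where the two are correlated, leaving the baseline score out makes the comparison of the arms less precise than the collected data allow. Diagnoses from the shoulder to the small finger joints may also differ in their usual pain level, which adds spread to the pooled comparison.

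The stake is largest in the single-diagnosis analyses, which are small. A second stake is the form of the result. The sample size rests on a difference in VAS points and the plan promises confidence intervals, but a Mann-Whitney test as named yields neither a difference in points nor an interval.

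**Working it through.** **Inputs from the Statistical Analysis section.** Difference 1 VAS point; SD 2; two-sided 0.05; 63 patients per diagnosis; 1000 in total.

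**Assumed, because not stated.** 80% power for the plan's own calculation; 1:1 allocation; r from 0 to 0.5.

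**1. The plan's figure.** n per arm = 2 × (1.960 + 0.842)² × 2² / 1² = 62.8, so 63. The stated number is therefore a per-arm number, although it is written as the number of patients for each diagnosis. Both readings are carried below: 31/32 per arm (63 in total) and 63 per arm.

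**2. Power with linear ANCOVA on baseline VAS.** The variance of the adjusted difference is

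4 × (1 − r²) × (1/n1 + 1/n2) × (1 + F/(n − 2)),

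where n = n1 + n2 and F follows an F(1, n − 2) distribution. The last factor allows for chance imbalance at baseline and averages 1.017 at 31/32 and 1.008 at 63/63. Power is from the noncentral t distribution with n − 3 degrees of freedom, averaged over F.

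| Per arm | Unadjusted t test | r = 0 | r = 0.3 | r = 0.5 |
|---|---|---|---|---|
| 31/32 | 49.7% | 49.1% | 52.8% | 60.9% |
| 63/63 | 79.5% | 79.2% | 82.8% | 89.3% |

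Adjustment breaks even at r = 0.13 (31/32) and r = 0.09 (63/63). The 95% CI half-width at 31/32 goes from 1.01 unadjusted to 1.02, 0.97 and 0.88 points at r = 0, 0.3 and 0.5.

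**3. All 1000 patients together (500/500).** Power for 1 point exceeds 99.99% without adjustment. The half-width goes from 0.248 to 0.237 at r = 0.3 and 0.215 at r = 0.5. A diagnosis term alone, if diagnosis explained 5%, 10% or 20% of the variance (assumed, 8 to 16 groups), would give about 0.244, 0.237 or 0.224.

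**4. Change score.** Its SD is 2 × √(2(1 − r)), which exceeds 2 whenever r is below 0.5. Power at 31/32 is 28.2%, 37.9% and 49.7% at r = 0, 0.3 and 0.5, so it never beats the raw score in this range.

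**5. Against the test actually named.** Simulation at 31/32 per arm: 20,000 runs per setting (simulation error about 0.35 percentage points), whole-number scores on 0 to 10, mean 4.5, SD 2, effect −1. The shapes are assumed: normal or shifted gamma. The Mann-Whitney column gives the range over all r tried. The other columns give power at r = 0 / 0.3 / 0.5.

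| Skewness | Mann-Whitney | Linear ANCOVA | Rank ANCOVA |
|---|---|---|---|
| 0 | 46.2–47.5% | 48.0 / 51.4 / 59.1% | 46.7 / 49.8 / 56.7% |
| 1.0 | 53.5–54.6% | 49.8 / 53.7 / 60.9% | 53.8 / 57.6 / 64.5% |
| 1.4 | 59.7–60.9% | 50.8 / 54.0 / 61.5% | 60.7 / 63.3 / 71.4% |

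Type I error was 0.045 to 0.052 for all three methods. Rank ANCOVA matches Mann-Whitney at r = 0 and is ahead from r = 0.3 in every shape. Linear ANCOVA trails Mann-Whitney by about 6 to 10 points at skewness 1.4 when r is 0.3 or less.

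**The case against.** The strongest case against has five parts.

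- **The gain may be nothing.** The powered outcome is pain while the injection is given, which may be mostly procedural and only weakly related to earlier pain. Even at r = 0.3 a 63-patient diagnosis group moves only from 49.7% to 52.8%. This stands, and it is why the point is optional.
- **Linear ANCOVA can lose to the rank test already named.** This stands. The plan allows for non-normal data, and raw-score ANCOVA should not be the sole primary test.
- **The quoted test may not be the test of the primary outcome.** This stands. Outcome Measures separates pain before, at and after the injection, post-injection VAS is not defined, and nothing shows that it is the same measure as the powered outcome.
- **An estimate in VAS points does not require ANCOVA.** This stands in part. The t test gives a mean difference with an interval, and a Hodges-Lehmann interval could accompany Mann-Whitney, though the plan does not say that either will be reported for the primary outcome.
- **Diagnosis is not ignored.** Subgroup analyses are planned, and the fourth objective looks at type of injury and affected joint. This stands; the gap is only in the analysis of all patients together.

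A reader might infer that the unadjusted comparison is biased or invalid. The documents do not support that: patients are randomised from a computer-generated concealed sequence, and no stratification is described that would oblige a diagnosis term. A reader might also infer that the signed-rank test already uses the baseline. Read as before against after, it would do so only within an arm; as written, it is described as comparing the arms.

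**Conclusion.** The point holds as an optional improvement. A baseline score that will be collected anyway is not used to compare the arms, and the pooled analysis has no diagnosis term. Against the t test, adjustment costs at most about 0.7 percentage points of power and gains about 3 points at r = 0.3 and 10 to 11 points at r = 0.5. In the pooled analysis the benefit is confined to a slightly narrower interval.

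These figures rest on an r that the documents do not give, on SD 2 and 1:1 allocation, and, for the rank methods, on assumed score shapes. Rank ANCOVA was simulated at 31/32 without a diagnosis term, and VAS at 6 weeks was not calculated separately.

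It would be wrong to conclude that adjustment rescues the sample size. It does not repair the use of 63, a per-arm number, as the size for each diagnosis. Nor does it repair the SD: the quoted SEM of 0.4 with 30 per group implies 0.4 × √30 = 2.19 rather than 2, which alone lowers unadjusted power to about 43% at 31/32 and 72% at 63 per arm.

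**What to change.** 1. State which measurement post-injection VAS is, and whether it is the primary outcome.
2. For the hypothesis test, replace the unadjusted Mann-Whitney test with a rank ANCOVA: ranked VAS on arm and ranked pre-injection VAS.
3. In the pooled analysis add diagnosis group, with small groups combined by a stated rule, because the list of eligible diagnoses is open-ended.
4. Report alongside it, as the estimate, the linear ANCOVA adjusted difference in VAS points with its 95% CI. Do not make this the sole primary test.
5. Use the baseline as a covariate; do not analyse change scores.
6. Say whether the covariate is VAS at rest or on active movement, and how a missing pre-injection VAS is handled.

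The cost is SAP wording and adding primary diagnosis to the variable list, which the planned subgroup analyses need in any case. No extra patients or visits are required.
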